4.0 TREATMENT PLAN

Patients will be treated with combination treatment consisting of brentuximab vedotin and rituximab infusions as detailed below. All patients will receive Induction treatment, and those who achieve response (PR or CR) may have an optional cycle of Consolidation treatment, identical to Induction. Maintenance will then continue for up to one year from the first dose of study treatment.

[figure not shown]

TABLE 1: Dosing Summary

	Induction (1 cycle = 4 weeks)	Consolidation* (1 cycle = 4 weeks)	Maintenance (1 cycle = 3 weeks)
Brentuximab Vedotin dosing	1.2 mg/kg IV over 30 mins Weekly x3	1.2 mg/kg IV over 30 mins Weekly x3	1.8 mg/kg IV over 30 mins Once every 3 weeks
Rituximab dosing	375 mg/m ² IV weekly x4	375 mg/m ² IV weekly x4	375 mg/m ² IV once every 6 weeks

*Optional for patients who achieve PR/CR during induction. See section 4.1.3 for stipulations regarding SD.

4.1 Treatment Dosage and Administration

NOTE: A baseline weight and height should be obtained on the first day of treatment for all patients, and weights should be checked at least once per cycle. Treatment dosages will be based upon most recent weight and BSA (preferably from that day of treatment). Dosing is to be subsequently modified if subject weight has changed by more than 10% or the BSA has changed more than 5%.

NOTE: The cycle lengths are as follows:

Induction: 4 weeks (28 days)
Consolidation: 4 weeks (28 days)
Maintenance: 3 weeks (21 days)

4.1.1 Phase I and II dosage:

Because both drugs are well-tolerated and carry low risks of clinically significant toxicity, patients in phase I were treated initially at the most commonly used doses of each drug according to the schedules outlined below. *NOTE: The dose*

for patients with a weight of >100 kg should be calculated for 100 kg (please refer to Section 8.1.6 for details):

The RP2D was established for Phase II on 3/12/2014, and dosing for both Phase I and Phase II is outlined below.

4.1.1.1 Brentuximab vedotin

Induction: 1.2 mg/kg IV infusion over 30 minutes, weekly x 3 (1 cycle = 4 weeks; no brentuximab vedotin is given during the fourth week)

Consolidation (optional): Identical to Induction. Those patients who achieve response (PR or CR) after the Induction course may receive an additional treatment of the same (termed Consolidation). In addition, any patients achieving CR to induction, in whom avoidance of Maintenance therapy is sought, can receive consolidation as their final planned therapy. See section 4.1.3 for stipulations regarding stable disease.

Maintenance: 1.8 mg/kg IV infusion over 30 minutes once every 3 weeks (1 cycle = 3 weeks), for a total of one year from the first induction dose or until progression of disease.

4.1.1.2 Rituximab

Induction: 375 mg/m² IV infusion per standard protocol, once weekly for 4 weeks (1 cycle = 4 weeks)

Consolidation (optional): Identical to Induction. Those patients who achieve response (PR or CR) after the Induction course may receive an additional treatment of the same (termed Consolidation). In addition, any patients achieving CR to induction, in whom avoidance of Maintenance therapy is sought, can receive consolidation as their final planned therapy. See section 4.1.3 for stipulations regarding stable disease.

Maintenance: 375 mg/m² IV infusion per standard protocol, once every 6 weeks for a total of one year from the first induction dose or until progression of disease.

4.1.1.2.1 Pre-Registration Rituximab

Patients may receive one dose of rituximab prior to registration as specified in 3.1.3. In such cases, the patient will receive a total of four rituximab doses during Induction, with only 3 doses given as part of Induction treatment (weekly, along with brentuximab vedotin).

4.1.1.3 It is intended that all treatments will be administered on an outpatient basis. However, treatment can be initiated during hospitalization (i.e., for newly-diagnosed patients), and can continue during unforeseen hospitalizations, but only at the discretion of the local PI.

4.1.1.4 When both agents are to be administered on the same day, rituximab will be given immediately before brentuximab vedotin. No specific time interval is required between dosing of the agents (for either Phase I or Phase II). In other words, one can be given immediately after the other.

4.1.2 Phase I treatment plan:

The DLT detection period will be the first 21 days of treatment, starting on day 1 of induction. The first three patients enrolled on the study will be treated as a single cohort at the doses described above. If none of these first three (0/3) patients experience a DLT (defined below), this will constitute the RP2D.

In the event of 1 DLT among the first 3-patient cohort (1/3), an expansion cohort of an additional three patients will be treated at the same dose. Of the second 3 patients treated, if no additional patients experience DLT (ie, DLT in 1/6 patients), RP2D will not be changed.

In the event of 2 or 3 DLT among the first 3-patient cohort, or in the event that an expansion cohort is required and results in 2 or more DLT among the 6 patients ($\geq 2/6$) treated in the first and expansion cohorts, dose de-escalation will be explored. De-escalation will consist of brentuximab vedotin at 0.8 mg/kg, with the schedule otherwise unchanged, and with rituximab dose and schedule unchanged.

This dose de-escalation will be studied in a cohort of 3 patients, and if no DLT are observed, the study will commence at this lower dose. In the event that 1 or more DLT are observed at this dose reduction, enrollment will be held and the protocol reviewed.

4.1.3 **Phase II treatment:**

Treatment will be at the RP2D (see section 4.1.1), as determined by the means described above.

Induction: 1.2 mg/kg IV infusion over 30 minutes, weekly x 3 (1 cycle = 4 weeks; no brentuximab vedotin is given during the fourth week)

After First Re-Staging:

Patients achieving **PD** at first re-staging should be taken off treatment and treated with R-CHOP or similar chemotherapy at the discretion of the local treating investigator.

Patients achieving **SD** should likewise be taken off treatment and treated as above. However, at the discretion of the treating investigator, such patients may receive an additional treatment of the same termed "**Consolidation**".

Consolidation treatment is identical to Induction. If, after Consolidation treatment, these patients achieve CR or PR, they should proceed to Maintenance (see below for description). If, however, these patients are still SD or have progressed to PD, they should be taken off treatment and treated with R-CHOP or similar chemotherapy at the discretion of the local treating investigator.

Patients achieving **CR** or **PR** after the Induction course may receive an additional treatment of the same termed "**Consolidation**". Consolidation treatment is identical to Induction. For patients achieving CR after Induction, in whom avoidance of maintenance therapy is sought, Consolidation may be given as their final planned therapy. Patients who achieve CR after Induction may proceed directly to Maintenance therapy at the discretion of the treating investigator (for instance, if they are not likely to tolerate Consolidation therapy given the toxicity they experienced during Induction).

Following Consolidation, patients will proceed to **Maintenance:** 1.8 mg/kg IV infusion over 30 minutes once every 3 weeks (1 cycle = 3 weeks), for one year from starting induction or until progression of disease. At the discretion of the treating investigator, patients may discontinue brentuximab vedotin after 10 maintenance doses.

4.1.4 **Dose escalation on a per-patient basis (for both Phase I and Phase II):**

For any patient treated with a brentuximab vedotin dose of 0.8 mg/kg for 2 or more 21-day cycles without DLT, subsequent doses can be increased to 1.2 mg/kg, **but only at the discretion of the treating investigator.** *NOTE: the*

basis for escalation, or lack thereof, should be clearly documented in the Treatment eCRF.

4.1.5 Recommended treatment off study in the event of progressive disease or loss of response:

Clinical suspicion of progressive disease (PD) or loss of response should be investigated radiographically, and if confirmed, will result in removal from active therapy (though any such patient will remain in study follow up; see 4.5, Duration of Therapy). In this case, it is strongly recommended that investigators consider early initiation R-CHOP or similar chemoimmunotherapy (off trial).

4.1.6 Administration details

Table 2 below summarizes the administration of both agents.

TABLE 2: Regimen Detail					
Agent	Premedications*	Dose	Route	Schedule[^]	Duration
Rituximab	30 min prior: Tylenol 650 mg PO Benadryl 50 mg IVPB PRN for infusion reactions: Solumedrol 125 mg IV over 15 min	375 mg/m ²	IV per standard protocol (see below)	Weekly x 4	4 weeks [¥]
		375mg/m ²	IV per standard protocol (see below)	Every 6 weeks	1 year or until POD
Brentuximab vedotin		1.2 mg/kg [¥]	IV over 30 min [¥]	Weekly x 3 (4 th week off) [¥]	3 weeks [¥]
		1.8 mg/kg	IV over 30 min	Every 3 weeks	1 year or until POD

*Premedication protocol is the same regardless of which drug is used, and will be used only once when both drugs are administered on the same day, unless \geq 4 hours passes between start of rituximab infusion and that of brentuximab vedotin, in which case the same premedication protocol can be administered again prior to the start of the second study agent, at the discretion of the treating investigator.

[¥]The parameters specified in the shaded boxes represent the Induction phase and the optional Consolidation phase, the latter of which is optional (see sections 4.1.1.1 and 4.1.1.2). The non-shaded boxes represent the maintenance phase.

[^]During Induction and the optional Consolidation phase, 1 cycle = 4 weeks; during maintenance therapy, 1 cycle = 3 weeks

4.1.6.1 Rituximab Administration Guidelines:

DO NOT ADMINISTER AS AN IV PUSH OR BOLUS. Premedicate before each infusion. Administer only as an IV infusion.

4.1.6.1.1 First Infusion:

Initiate infusion at a rate of 50 mg/hr. In the absence of infusion toxicity, increase infusion rate by 50 mg/hr increments every 30 minutes, to a maximum of 400 mg/hr.

4.1.6.1.2 Subsequent Infusions:

Initiate infusion at a rate of 100 mg/hr. In the absence of infusion toxicity, increase rate by 100 mg/hr increments at 30-minute intervals, to a maximum of 400 mg/hr. Interrupt the infusion or slow the infusion rate for infusion reactions.

Continue the infusion at one-half the previous rate upon improvement of symptoms.

At the discretion of the treating investigator, rapid rituximab infusion is allowable after the first dose, if the initial dose was well-tolerated.

4.2 Dose-Limiting Toxicity (DLT) and Maximally Tolerated Dose (MTD):

For Phase I, DLT evaluation will occur weekly during the first 21 days of induction. (Adverse events, however, will continue to be collected for the duration of treatment). In general, a non-hematologic DLT is defined as any Grade ≥ 3 toxicity, and a hematologic DLT is defined as any Grade ≥ 4 toxicity, both by CTCAE v4.03 criteria. In addition, the following criteria and exceptions apply:

- 4.2.1 ANC $< 500/\text{mm}^3$ for > 14 days despite GCSF support is a DLT.
- 4.2.2 Platelet count $< 20,000/\text{mm}^3$ that is considered drug-related is a DLT.
- 4.2.3 For nausea, vomiting, or diarrhea, patients must have Grade 3 or 4 toxicity that persists at this level despite use of optimal symptomatic treatment, in order for these to be considered a DLT.
- 4.2.4 Grade 3 thromboembolic events are not considered DLT.
- 4.2.5 Any Grade 3 rash that resolves to Grade ≤ 2 within a 10 day period (including with symptomatic treatment) will not be considered a DLT.
- 4.2.6 Cases involving hyperbilirubinemia that is primarily indirect, and considered not reflective of underlying liver disease (ie, resulting from transfusion of red blood cells), will not be considered a DLT.

4.3 Toxicities and Dosing Delays/Dose Modifications

All patients receiving at least one treatment on this protocol will be evaluable for toxicity. Each patient will be assessed for the development of toxicity according to the Time and Events Table (See Section 6.4). Toxicity will be assessed according to the CTCAE v 4.03, and pre-dose lab values must be assessed prior to dosing at each treatment visit. Dose adjustments should be made according to the system showing the greatest degree of toxicity.

Treatment modifications and dosing delays are to follow in Tables 3 and 4 below. For the phase I component, those events constituting a DLT also warrant treatment/modification as outlined below. In the event that both study agents could be responsible for a given toxicity, the treating investigator should first modify only the dose of the most likely offending agent; brentuximab vedotin should be adjusted before that of rituximab, as most toxicities are more common with this agent. Study treatment should not be delayed but rather, skipped & not be made up. Cycles should not be extended, if possible. If the dose of brentuximab vedotin is skipped or decreased due to toxicity, the dose may be restarted or increased for that individual patient in the event that the toxicity resolves completely (at the treating investigator's discretion).

Please also refer to sections of this protocol that contain more detailed information on the potential adverse events and risks associated with each agent (Sections 1.2.1.1 and 1.2.2.1). Any patient missing more than 3 consecutive administrations due to toxicity must be removed from the study. Doses reduced per protocol due to occurrence of adverse events are not counted as missed doses.

TABLE 3a: Drug-Related Hematological Toxicity Dose Reductions for Brentuximab vedotin - ANC

ANC	Action
$\geq 1,500/\mu\text{L}$	None.
1000-1499/ μL	
-1st Occurrence: Withhold current dose until ANC $\geq 1,500/\mu\text{L}$ and platelets $\geq 100,000/\mu\text{L}$. Do not replace missed doses. Restart next treatment at previous dose.
 
-2nd Occurrence: Withhold current dose until ANC $\geq 1,500/\mu\text{L}$ and platelets $\geq 100,000/\mu\text{L}$. Do not replace missed doses. Restart next treatment at 50% previous dose.
 
-3rd Occurrence: Withhold current dose until ANC $\geq 1,500/\mu\text{L}$ and platelets $\geq 100,000/\mu\text{L}$. Do not replace missed doses. Restart next treatment at 25% previous dose.
 
-4th Occurrence: Discontinue protocol therapy.

500-999/ μL	
-1st Occurrence: Notify treating investigator. Withhold current dose until ANC $\geq 1,500/\mu\text{L}$ and platelets $\geq 100,000/\mu\text{L}$. Do not replace missed doses. Restart next treatment at 50% previous dose.
 
-2nd Occurrence: Withhold current dose until ANC $\geq 1,500/\mu\text{L}$ and platelets $\geq 100,000/\mu\text{L}$. Do not replace missed doses. Restart next treatment at 25% previous dose.
 
-3rd Occurrence: Discontinue protocol therapy.

<500/ μL	
-1st Occurrence: Withhold current dose until ANC $\geq 1,500/\mu\text{L}$ and platelets $\geq 100,000/\mu\text{L}$. Restart next treatment at 25% previous dose.
 
-2nd Occurrence: Discontinue protocol therapy.

*G-CSF (Filgrastim), including Neulasta®, may be added for low ANC while a dose reduction is instituted at treating physician's discretions.

TABLE 3b: Drug-Related Hematological Toxicity Dose Reductions for Brentuximab vedotin - Platelets

Platelets	Action
100,000/ μL	None.
75,000-99,000/ μL	
-1st Occurrence: Withhold current dose until ANC $\geq 1,500/\mu\text{L}$ and platelets $\geq 100,000/\mu\text{L}$. Do not replace missed doses. Restart next treatment at previous dose.
 
-2nd Occurrence: Withhold current dose until ANC $\geq 1,500/\mu\text{L}$ and platelets $\geq 100,000/\mu\text{L}$. Do not replace missed doses. Restart next treatment at 50% previous dose.
 
-3rd Occurrence: Withhold current dose until ANC $\geq 1,500/\mu\text{L}$ and platelets $\geq 100,000/\mu\text{L}$. Do not replace missed doses. Restart next treatment at 25% previous dose.
 
-4th Occurrence: Discontinue protocol therapy.

50,000-74,000/ μL	
-1st Occurrence: Notify treating investigator. Withhold current dose until ANC $\geq 1,500/\mu\text{L}$ and platelets $\geq 100,000/\mu\text{L}$. Do not replace missed doses. Restart next treatment at 50% previous dose.
 
-2nd Occurrence: Withhold current dose until ANC $\geq 1,500/\mu\text{L}$ and platelets $\geq 100,000/\mu\text{L}$. Do not replace missed doses. Restart next treatment at 25% previous dose.
 
-3rd Occurrence: Discontinue protocol therapy.

<50,000/ μL	
-1st Occurrence: Withhold current dose until ANC $\geq 1,500/\mu\text{L}$ and platelets $\geq 100,000/\mu\text{L}$. Restart next treatment at 25% previous dose.
 
-2nd Occurrence: Discontinue protocol therapy.

TABLE 4 Drug-Related Non-Hematological Toxicity Dose Reductions for Brentuximab vedotin & Rituximab ¹

CTCAE v 4.03 Grade	Brentuximab vedotin	Rituximab
0-2	No change from original starting dose	No change from original starting dose
3-4	Skip treatment until resolved to \leq Grade 2, then reduce by 33%	May continue if toxicity is clinically attributed to brentuximab vedotin. Otherwise, skip treatment until resolved to \leq Grade 2, then resume at same dose
Second episode of grade 3 or 4 toxicity	Skip treatment until resolved to \leq Grade 2, then reduce by 33%	May continue if toxicity is clinically attributed to brentuximab vedotin. Otherwise, skip treatment until resolved to \leq Grade 2, then resume at same dose
Third episode of grade 3 or 4 toxicity	Remove subject from trial	Remove subject from trial

¹ This table should be followed for all non-hematological toxicities EXCEPT peripheral neuropathy, hyperamylasemia, and pancreatitis, which should be managed as outlined below. In cases involving hyperbilirubinemia that is primarily indirect, and considered not reflective of underlying liver disease (ie, resulting from transfusion of red blood cells), treating investigators may consider avoiding protocol-specified dose reductions, after consultation with principal investigator.

Management of peripheral neuropathy:

- For new or worsening Grade 2 or 3 peripheral neuropathy, brentuximab vedotin should be withheld until neuropathy improves to Grade 1 or baseline and then restarted at a dose of 1.2 mg/kg. Missed doses will not be made up.
- For grade 4 peripheral neuropathy, discontinue treatment with brentuximab vedotin.

Dose modifications regarding hyperamylasemia and pancreatitis

- Asymptomatic elevated amylase and lipase (for patients with amylase elevation $>3x$ upper limit of normal, but no abdominal pain):
 - Grade 1 – continue at same dose level
 - Grade 2 – continue at same dose level
 - Grade 3 – withhold treatment until toxicity resolves to \leq Grade 2 and then resume treatment at the same dose level. Missed doses will not be made up.
 - Grade 4 – withhold treatment until toxicity resolves to \leq Grade 2 and then resume treatment at reduced dose level or discontinue at the discretion of the treating investigator
- Mild to moderate pancreatitis (hyperamylasemia syndrome – characterized by abdominal pain of <72 hours duration with amylase and/or lipase elevation): Withhold brentuximab vedotin. May consider resuming, with 1 dose level reduction, when signs, symptoms and laboratory values (i.e., amylase and lipase) return to baseline/normalize. If a 2nd episode of mild to moderate pancreatitis occurs, brentuximab vedotin must be permanently discontinued. Missed doses will not be made up.
- Severe pancreatitis (abdominal pain of 72 hours and amylase elevation of 3x normal for > 72 hours duration): Permanently discontinue brentuximab vedotin.

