1.2.1.10.3 Relapsed/refractory CD30+ malignancies

The safety and efficacy of weekly dosing of brentuximab vedotin was also evaluated in patients with relapsed and refractory CD30+ hematologic malignancies [21]. The agent was administered intravenously on Days 1, 8, and 15, of each 28-day cycle at doses ranging from 0.4 to 1.4 mg/kg, with doses escalated in increments of 0.2 mg/kg until dose-limiting toxicity (DLT) was observed. The MTD was 1.2 mg/kg. The most common adverse events were peripheral sensory neuropathy, fatigue, nausea, diarrhea, arthralgia, and pyrexia; and the majority of events were mild to moderate in severity. Tumor regression occurred in 85% of patients and the overall objective response rate was 59% (n = 24), with 34% (n = 14) complete remissions. We are using this data as rationale for weekly induction therapy of brentuximab vedotin.

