8.1.6.2 Dilution

Calculate the required volume of 5 mg/mL reconstituted ADCETRIS® solution needed and withdraw this amount from the vials. The dose for patients with a weight of >100 kg should be calculated for 100 kg. Immediately add the reconstituted solution to an infusion bag containing a minimum volume of 100 mL to achieve a final concentration of 0.4 mg/mL to 1.8 mg/mL brentuximab vedotin. ADCETRIS® can be diluted into 0.9% Sodium Chloride Injection, 5% Dextrose Injection or Lactated Ringer's Injection. Gently invert the bag to mix the solution. ADCETRIS® contains no bacteriostatic preservatives. Following dilution, infuse the ADCETRIS® solution immediately, or store the solution at 2-8°C (36-46°F) and use within 24 hours of reconstitution. DO NOT FREEZE.

8.1.7 **Route of administration for this study**

Intravenous infusion.

8.1.8 **Incompatibilities:**

Brentuximab vedotin is not to be mixed with, or administered as an infusion with, other medicinal products. (The only exception is that it may be co-administered, but not mixed with, rituximab, when administered as part of this clinical trial.)

8.1.9 **Availability**

Brentuximab vedotin will be supplied by the study supporter, Seattle Genetics. This drug may be ordered by completing the Investigational Drug Request/Shipment Record Form (see Appendix B), which then may be faxed or emailed as directed on the Form.

8.1.10 **Side effects:**

The most common adverse reactions (≥20%), regardless of causality, were neutropenia, peripheral sensory neuropathy, fatigue, nausea, upper respiratory tract infection, diarrhea, pyrexia, and vomiting.

Less commonly progressive multifocal leukoencephalopathy (PML), Stevens-Johnson syndrome (SJS), toxic epidermal necrolysis (TEN), tumor lysis syndrome (TLS), acute pancreatitis, pulmonary toxicity, and hepatotoxicity.

NOTE: Current safety data are based on oncology studies (see section 1.2.1). As a result, 1.8mg/kg is the recommended dose for approved indications.

8.1.11 **Return and Retention of Study Drug**

It is NOT expected that excess drug will be returned to the manufacturer, and it is asked that sites destroy drug remaining at the end of the study per their local policy. The manufacturer will provide memos with lot number and expiration dates, and expired drug may also be destroyed per local policy.

8.1.12 **Nursing/patient implications**

- Avoid use in patients with severe renal impairment

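### The 25% dose-reduction step in Tables 3a and 3b cannot be prepared within the protocol's own dilution limits during weekly dosing, and the base of the percentage is undefined

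*Combined protocol and SAP*

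**What the plan says.** **Starting doses.** Section 4.1.1.1 gives "1.2 mg/kg IV infusion over 30 minutes, weekly x 3" for Induction and the optional Consolidation, and "1.8 mg/kg IV infusion over 30 minutes once every 3 weeks" for Maintenance.

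**Reductions.** Tables 3a (ANC) and 3b (platelets) in section 4.3 have three bands of increasing severity, and every row first withholds the dose.
- Mildest band, first three occurrences: "Restart next treatment at previous dose", then "Restart next treatment at 50% previous dose", then "Restart next treatment at 25% previous dose".
- Middle band, first two occurrences: the 50% step, then the 25% step.
- Most severe band (ANC below 500/µL, platelets below 50,000/µL): the 25% step at the first occurrence.

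**Preparation.** Section 8.1.6.2 requires an "infusion bag containing a minimum volume of 100 mL to achieve a final concentration of 0.4 mg/mL to 1.8 mg/mL brentuximab vedotin". Sections 4.1.1, 8.1.6.1 and 8.1.6.2 calculate the dose for 100 kg in any heavier patient.

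**Lowest dose cited.** Section 1.2.1.10.3 describes a weekly-dosing study "at doses ranging from 0.4 to 1.4 mg/kg".

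**Re-increase.** Section 4.3 lets the treating investigator raise a decreased dose if the toxicity resolves completely.

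**The concern.** A minimum bag volume together with a minimum concentration sets a minimum dose in milligrams. The reduction tables give percentages without reference to that minimum and set no floor. If a prescribed step falls below it, the pharmacy must either breach the preparation text or depart from the dose table. Sites may resolve this differently.

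The base of the percentage is a second gap. In the first-occurrence row of the mildest band, previous dose can only mean the dose in use before the hold. Carried down the column, that makes successive percentages multiply. A site that instead reads the column as 100%, 50% and 25% of the starting dose would give a different amount to the same patient. No section settles this, or says how a reduced weekly dose carries into Maintenance.

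At stake are whether the dosing instruction for the investigational drug can be carried out, and whether sites deliver the same dose for the same blood count.

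**Working it through.** **Inputs.** 1.2 mg/kg weekly and 1.8 mg/kg every 3 weeks (4.1.1.1). Steps of 50% and 25% (Tables 3a and 3b). Bag of at least 100 mL, 0.4 to 1.8 mg/mL (8.1.6.2). Weight cap of 100 kg (8.1.6.2). Reconstituted strength 5 mg/mL (8.1.6.1).

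**Formulas.** Dose in mg = mg/kg × weight, with weight at most 100 kg. Highest achievable concentration = dose / 100 mL, because a larger bag only lowers it.

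**Reproducing the plan's own figure.** 1.8 mg/kg × 100 kg = 180 mg, and 180 / 100 = 1.8 mg/mL. This is exactly the stated upper limit, so the limits and the weight cap are being applied as the protocol intends.

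**Smallest dose that complies.** 0.4 mg/mL × 100 mL = 40 mg. The weight needed is 40 / (mg/kg).

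| Step | mg/kg | 70 kg: mg (mg/mL) | 100 kg: mg (mg/mL) | Weight needed for 40 mg |
|---|---|---|---|---|
| 50% of 1.2 | 0.60 | 42 (0.42) | 60 (0.60) | 66.7 kg |
| 25% of 1.2 | 0.30 | 21 (0.21) | 30 (0.30) | 133.3 kg, above the cap |
| 50% then 25%, from 1.2 | 0.15 | 10.5 (0.105) | 15 (0.15) | 266.7 kg, above the cap |
| 50% of 1.8 | 0.90 | 63 (0.63) | 90 (0.90) | 44.4 kg |
| 25% of 1.8 | 0.45 | 31.5 (0.315) | 45 (0.45) | 88.9 kg |
| 50% then 25%, from 1.8 | 0.225 | 15.75 (0.158) | 22.5 (0.225) | 177.8 kg, above the cap |

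**Sensitivity to added volume.** If the 5 mg/mL solution adds to the bag volume, concentration = dose / (100 + dose/5), and the smallest complying dose is 40 / (1 − 0.4/5) = 43.5 mg. Then 25% of 1.2 mg/kg at 100 kg gives 30 / 106 = 0.283 mg/mL. The weights needed rise to 72.5 kg for 0.60 mg/kg and 96.6 kg for 0.45 mg/kg. The conflict becomes slightly wider.

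**Can the key step arise in weekly dosing?** Yes. A patient with a first ANC below 500/µL before the second Induction dose, recovered by the third, is due 0.30 mg/kg at the third. No compounding is needed.

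**Base of the percentage.** Literal reading: 0.50 × 0.25 = 0.125 of the starting dose. Starting-dose reading: 0.25. The ratio is 2, that is 0.15 against 0.30 mg/kg from the weekly dose, and 0.225 against 0.45 mg/kg from the Maintenance dose. Both compounded doses are below 0.4 mg/kg, the lowest dose cited. So is 0.30 mg/kg, but 0.45 mg/kg is not.

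**The case against.** **Compounding is not certain, and it can be interrupted.** A 100/50/25 ladder from the dose before toxicity is a plausible intention, and section 4.3 permits a re-increase. This has force against the 0.15 and 0.225 mg/kg figures, which rest on the literal reading. It does not touch the central conflict, because 25% of 1.2 mg/kg fails without compounding. The re-increase is discretionary, sets no floor, and does not make the prescribed restart dose preparable.

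**The step may be rare.** The documents give no frequency for these bands under this regimen. Section 1.2.1.1 reports dose delays for neutropenia in 14% of patients on monotherapy, which is not an estimate for this step, and Table 3a allows G-CSF. The objection stands as a limit on how many patients are affected. It does not make the instruction executable.

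**Stronger readings that a reader might infer, and that the documents do not support:**
- *Three mild ANC dips within Induction lead to 0.15 mg/kg.* Induction has only three brentuximab doses, each occurrence withholds one, and skipped doses are not made up. No Induction dose is left for that step. A compounded weekly dose would need a route running into Consolidation.
- *25% could mean a cut of 25%, so sites could differ three-fold.* Table 4 says reduce by when it means a decrement. A 25% cut would also restart the most severe band at 75% and the middle band at 50%, which reverses the order of severity.
- *Every reduced dose is below anything the protocol cites.* This is false for 25% of 1.8 mg/kg (0.45 mg/kg).
- *The response analysis or the recommended phase II dose is compromised.* Each reduction first skips a dose that is not replaced, so such a patient does not reach the three doses required by section 6.2.1.1 on Induction alone. Section 4.1.1 records that the recommended dose was already set on 3/12/2014.

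**Conclusion.** The dosing tables are wrong as written, because they cannot be followed together with section 8.1.6.2. During weekly dosing, the 25% step reaches at most 30 mg against a minimum of 40 mg, at every allowed weight and whether or not reductions compound. It is triggered by a single severe count. Two further steps fail by weight: 25% of 1.8 mg/kg below about 89 kg, and 50% of 1.2 mg/kg below about 67 kg. These thresholds ignore added drug volume, and counting it raises them.

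Separately, the undefined base leaves a two-fold difference between readings after successive reductions, with the literal reading giving doses that cannot be prepared at any allowed weight.

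The conclusion assumes that 25% previous dose means a quarter of that dose, which the wording of Table 4 and the order of severity support. The effect is on whether the instruction can be carried out and on consistency between sites. Sample size, power and error rates do not change. The documents do not show which passage should give way.

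**What to change.** Reconcile Tables 3a and 3b with section 8.1.6.2 in a protocol amendment.
- State whether each percentage refers to the protocol dose for that phase or to the last dose given.
- Express each step explicitly for the weekly phases and for Maintenance, and say how a reduced weekly dose carries into Maintenance.
- Have pharmacy confirm that each step can be prepared within the stated bag volume and concentration across the eligible weight range, or revise the preparation text with appropriate support.

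The sponsor chooses the values and decides which passage changes; this review proposes none. The cost is a table edit and a pharmacy check, with no extra patients or visits and no change to the design.
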